#### 8.7 Criteria for stopping the study

The events listed below are the stopping rules for the study. In the case of any of these events, no additional patients will be recruited, dosed or imaged until the issue is resolved.

- Recommendation by the Data Safety Monitoring Board after evaluation of cumulative safety reviews
- Any death probably or definitely related to the treatment with LUM015 or the Imaging Device.
- Any other event that is deemed unacceptable in nature, severity, or frequency as assessed by the Investigator.
- Allergic reactions of Grade 3 or greater as defined in CTCEA 5.0

In the case that a safety event requiring enrollment suspension occurs, a prompt cumulative review of safety data and the circumstances of the event in question will be conducted to determine whether recruitment can be resumed, whether the protocol should be modified, or whether the study will be discontinued permanently. The FDA and reviewing IRB must be notified of any event that triggers suspension of enrollment in this study. If enrollment is suspended for safety reasons and it is deemed appropriate to resume the study, approval from the FDA and IRB must be obtained prior to resuming the study.

Regardless of whether recruitment is continued or not, all subjects injected with LUM015 or who were imaged with the LUM device at the time stopping rules were met will continue to be followed for safety.

In addition to the safety stopping rules outlined above, Luminell may suspend or terminate this study at any time. The reasons for temporarily suspending or terminating the study may include but are not limited to the following:

- Subject enrollment is unsatisfactory

LUMICELL CONFIDENTIAL

This document is confidential. Do not disclose or use except as authorized.

- Non-compliance that might significantly jeopardize the validity or integrity of the study.
- Luminicell decision to terminate development.

## 9 LUM015 FORMULATION AND ADMINISTRATION

### 9.1 Description

LUM015 has an abbreviated chemical formula of QSY21-Ahx-GGRK(Cy5)-AEEAc-C(mPEG20,000), where QSY21 is a fluorescence quencher from Life Technologies, Ahx is aminocaproic acid, G is the amino acid glycine, R is the amino acid arginine, K(Cy5) is the amino acid lysine conjugated with the fluorescent dye Cy5 (GE Healthcare), AEEAc is amino-ethoxy-ethoxy-acetyl, C is the amino acid cysteine and mPEG20,000 is a chain of methoxy-polyethylene glycol with an average molecular weight of 20,000 g/mol. The appearance of LUM015 is blue. The molecular weight of LUM015 is approximately 22,000 g/mol.

### 9.2 Form

LUM015 is supplied in 3-mL vials in powder form containing approximately 10 mg of LUM015, 10 mg of mannitol, 0.83 mg of sodium phosphate monobasic and 0.43 mg of sodium phosphate dibasic. LUM015 is provided by Luminicell, Inc.

### 9.3 Storage and stability

LUM015 must be stored at a temperature less than or equal to -20 °C (freezer) in powder form in the dark. Under these conditions, LUM015 is expected to be stable for up to 5 years. After reconstitution, LUM015 should be administered to the patient within 4 hours when stored at room temperature or 24 hours when stored refrigerated between 2°C and 8°C. Temperature logs are required for the storage freezers and refrigerators at the site's pharmacy.

### 9.4 Compatibility

Prior to injection, LUM015 should be reconstituted with 1.0 mL of 0.45% saline without glucose.

### 9.5 Handling

LUM015 should only be handled by qualified personnel familiar with procedures for reconstituting and injecting drugs or agents. Exposure to direct light for more than 5 minutes should be avoided.

### 9.6 Availability

LUM015 is an investigational agent and will be supplied free-of-charge from Luminicell, Inc.

### 9.7 Preparation

LUM015 is provided in amber vials in lyophilized form. Nominally each vial contains 10 mg of LUM015, 10 mg of mannitol, 0.83 mg of sodium phosphate monobasic and 0.43 mg of sodium phosphate dibasic. LUM015 will be reconstituted by adding 1.0 mL of 0.45% saline without glucose. Detailed preparation of the injection dose is explained in Appendix A. LUM015 from a single lot should be reconstituted for a given patient. Upon reconstitution, the pH of the solution is 6.5 and the osmolarity is 270 m-osm/L.

LUMICELL CONFIDENTIAL

This document is confidential. Do not disclose or use except as authorized.

Any reconstituted drug left in the vial that is not used for injection should be stored at 2-8 degrees C until it is confirmed that the patient did not exhibit an allergic reaction to the injection of LUM015. If an allergic reaction is reported, the remaining drug should be stored as -20 degrees C until a Luminell representative notifies your site of how to proceed with the vial.

## 9.8 Administration

LUM015 is administered as a single dose of 1.0 mg/kg via peripheral intravenous (IV) injection in 0.45% saline without glucose between 2 and 6 hours prior to surgery. The IV line must be flushed with 10-20 mL of saline just prior to injection of LUM015 and the injection is immediately followed by a saline flush of 10-20 mL. If extravasation is suspected or confirmed, the injection must be stopped immediately and reported to Luminell.

Per Principal Investigator's discretion, in order to protect subjects from potential anaphylactic reaction, prophylactic treatment with diphenhydramine and/or steroids may be administered.

In case of an allergic reaction to LUM015, sites should not discard any residual drug remaining in the used syringe. The syringe/used drug should be stored at -20 degrees C until a Luminell representative notifies your site of how to proceed with the used syringe.

## 9.9 Ordering

LUM015 will be provided by Luminell in enough quantities to cover the anticipated number of patients at each site. When more supply of LUM015 is needed, authorized pharmacy staff will notify the Principal Investigator and Luminell. Luminell will then supply the required vials of LUM015 for completing the study.

[name] at Luminell shall be notified via email at [[contact]](mailto:[contact]) for ordering LUM015.

## 9.10 Accountability

The investigator, or a responsible party designated by the investigator, must maintain a careful record of the inventory and disposition of LUM015 and the imaging devices utilizing appropriate forms.

## 9.11 Receipt and return of LUM015 and the LUM Imaging Devices

A drug inventory will be maintained by the clinical site's pharmacy. The inventory will include details of the LUM015 received and a clear record of when dispensed and for which subjects. This inventory record shall indicate the quantity and disposition of all investigational materials on hand at any time during the study.

LUM Imaging Devices will be delivered and installed by Luminell personnel and Instructions for Use (IFU) will be provided. Luminell personnel will also train the clinical staff on using the LUM Imaging System. Each clinical site investigator will maintain a device accountability record to document receipt and return of the LUM Imaging Devices.

At the end of the study, unused supplies of LUM015 and the investigational devices must be returned to Luminell. A Luminell representative will advise you when to return the supplies, as well as the proper shipping methods. Any LUM015 destroyed according to institutional policies will be documented in the Drug Accountability Record Form.

LUMICELL CONFIDENTIAL

This document is confidential. Do not disclose or use except as authorized.

## 10 STUDY CALENDAR

Baseline evaluations are to be conducted within 8 weeks ( $\pm$  3 days) prior to subject enrollment (Day 1). All baseline assessments must be performed prior to administration of any study agent. The study calendar below applies to all subjects injected with LUM015 including those that do not undergo imaging due to any reason, including a failure in the LUM Imaging Device initialization.

Task	Baseline evaluation/screening	Day 1 / Enrollment	$\sim$ 2-14 days after surgery	Routine follow up visit
LUM015 administration			X	
Informed consent	X			
History	X			
Concurrent meds	X			
Physical exam (Ht, Wt, VS)	X			
Surgery/intraoperative imaging		X		
Histology margin assessment			X	
EKG	X			
CBC	X			X
Serum chemistry a	X			X
Adverse event/adverse device effect evaluation		X		X
Tumor measurements	X			X
Radiologic evaluation	X			
B-HCG	X b			

a: Albumin, alkaline phosphatase, total bilirubin, BUN, calcium, chloride, glucose, potassium, total protein, SGOT [AST], SGPT [ALT], sodium.

b: Serum pregnancy test (women of childbearing potential).

### 11.1 LUM015 pharmacokinetics

During the Phase 1 IND study, the first 3 eligible subjects were dosed at 0.5 mg/kg LUM015 and the second 3 subjects were dosed at 1.0 mg/kg LUM015, with both groups injected ~29 hours prior to surgery. Resected tissue was imaged with the LUM Imaging Device in the pathology suite. A comparison of pharmacokinetic data from the initial 6 subjects to preclinical mouse studies suggested that a higher tumor:normal signal ratio would be achieved if tissue was imaged 4-6 hours after injection. The next 3 subjects were injected with 1.0 mg/kg of LUM015 and followed by 3 subjects injected with 1.5 mg/kg of LUM015 and the final cohort of 3 subjects was injected with 0.5 mg/kg. These nine subjects were followed by surgical resection at approximately 6 hours after LUM015 injection (i.e. same day injection and surgery).

To evaluate the pharmacokinetic parameters of LUM015, plasma PK samples were collected at the following time-points: pre-dose, 10, 20 minutes, 1, 2, 4, 8, 12, 18, 22, and 48 hours post-dose. The 48-hour collection was optional. Analysis of LUM015 (as Frag 1 after trypsin digestion of plasma) and Fragment 1 (non-digested plasma) were measured by LC-MS/MS. Additional metabolites, Fragment 2 and Fragment 3 were measured by HPLC-fluorescence.

A non-compartmental approach within Win-Nonlin software was used for PK parameter estimation. Due to a relative complexity of the PK profile observed and data constraints inherent in the study (small number of patients per dose level, optional data from 22-48 hours), a compartmental modeling approach was not utilized. Out of the 15 subjects, the 48-hour time-point sample was collected in 9 patients. Thus, in order to make use of the wealth of data collected up to 22 hours (all 15 patients from the study), but also use potentially important 48-hour data from the limited set of 9 subjects, PK calculations were performed on both sets (22-hour and 48-hour) independently. A summary of the resulting PK parameters for LUM015 are presented in Table 2.

Table 2: Pharmacokinetic parameters for LUM015. SD = standard deviation.

PK Parameter	0.5 mg/kg	SD	1.0 mg/kg	SD	1.5 mg/kg	SD
T max [hr]	0.11	0.17	0.06	0.13	0.00	0.00
C max [ug/mL]	15.46	2.26	28.41	6.55	45.76	3.78
AUC last [ug mL-1 h]	78.36	12.91	159.65	45.94	252.08	57.98
T 1/2 [h]	5.21	1.33	5.08	0.86	5.42	0.67

The pharmacokinetic data support rapid clearance of LUM015. After 22 and 48 hours, only 5% and 2% of the parent drug remain in plasma, respectively. The PK data support a multi-phased profile with linear pharmacokinetics.

The results from the repeat dose toxicity study in dogs (performed by NCI) show that administration of 0.5 or 10.0 mg/kg of LUM015 intravenously once daily for seven consecutive days (8 total doses) did not cause any observable target organ toxicities. The only observable effect was hypersensitivity in several dogs.

The results from a repeat dose toxicity study in rabbits show that administration of 15 mg/kg of LUM015 intravenously one daily for seven consecutive days was well tolerated. The test article-related findings were limited to transient blue/green discoloration of the urine. There were no test article-related adverse events observed and no hypersensitivity seen.

Clinicians should be prepared for a possible allergic reaction to occur during each administration of LUM015. Standing orders should be in place in the event of an allergic reaction for immediate intervention including administration of diphenhydramine, prednisone or both. If a study subject develops a Grade 3 (or greater) allergic reaction as defined in CTCEA 5.0, Lumicell should be contacted within 24 hours of the event:

LUMICELL CONFIDENTIAL

This document is confidential. Do not disclose or use except as authorized.

To Luminicell:  
[name], PhD  
[contact]  
Email: [[contact]](mailto:[contact])  
[contact]

### 11.3 Expected adverse device effects (associated with the LUM Imaging System)

To date, 64 patients (15 in Phase A, 45 in Phase B, and 4 patients to date in Phase C) have been imaged intraoperatively with the LUM Imaging System with no observable adverse device effects (the one incident of anaphylaxis in Phase C was considered an SAE but not an adverse device effect). Based on observation to date, there are no known anticipated or expected adverse device effects.

## 12 ADVERSE EVENT REPORTING REQUIREMENTS

### 12.1 Definitions

#### 12.1.1 Adverse Event (AE)

An adverse event (AE) is any undesirable sign, symptom or medical condition or experience that develops or worsens in severity after starting the first dose of study treatment or any procedure specified in the protocol, even if the event is not considered to be related to the study. The severity of any possible AE observed will be classified per the grading established by the Common Terminology Criteria for Adverse Events (CTCAE) 5.0.

Abnormal laboratory values or diagnostic test results constitute adverse events only if they induce clinical signs or symptoms or require treatment or further diagnostic tests.

#### 12.1.2 Serious adverse event (SAE)

A serious adverse event (SAE) is any adverse event, occurring at any dose and regardless of causality that:

- Results in death
- Is life-threatening. Life-threatening means that the person was at immediate risk of death from the reaction as it occurred, i.e., it does not include a reaction which hypothetically might have caused death had it occurred in a more severe form.
- Requires or prolongs inpatient hospitalization (i.e., the event required at least a 24-hour hospitalization or prolonged a hospitalization beyond the expected length of stay). Hospitalization admissions and/or surgical operations scheduled to occur during the study period but planned prior to study entry are not considered SAEs if the illness or disease existed before the person was enrolled in the trial, provided that it did not deteriorate in an unexpected manner during the trial (e.g., surgery performed earlier than planned).
- Results in persistent or significant disability/incapacity. Disability is defined as a substantial disruption of a person's ability to conduct normal life functions.
- Is a congenital anomaly or birth defect; or

LUMICELL CONFIDENTIAL

This document is confidential. Do not disclose or use except as authorized.

- Is an important medical event when, based upon appropriate medical judgment, it may jeopardize the subject and require medical or surgical intervention to prevent one of the outcomes listed above. Examples of such medical events include allergic bronchospasm requiring intensive treatment in an emergency room or at home; blood dyscrasias or convulsions that do not result in inpatient hospitalization, or the development of drug dependency or drug abuse.

Events **not** considered to be serious adverse events are hospitalizations for:

- routine treatment or monitoring of the studied indication, not associated with any deterioration in condition, or for elective procedures
- elective or pre-planned treatment for a pre-existing condition that did not worsen
- respite care

#### 12.1.3 Adverse device effect (ADE)

An adverse device effect (ADE) is an adverse event which is at least possibly related to the device. ADEs are not considered serious adverse events.

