#### 12.1.4 Unanticipated adverse device effects (UADEs)

Unanticipated adverse device effect (UADE) is any serious adverse effect on health or safety or any life-threatening problem or death cause by or associated with, a device, if that effect, problem, or death was not previously identified in nature, severity, or degree of incidence in the investigation plan or application, or any other unanticipated serious problem associated with a device that relates to the rights, safety or welfare of subjects.

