#### 12.4.3 Non-serious adverse event and adverse device effect reporting

Non-serious adverse events and non-serious adverse device effects will be reported to Luminicell on the adverse events Case Report Forms.

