#### **13.4 Data Safety Monitoring Board**

An independent Data Safety Monitoring Board (DSMB) will be established to review the safety of the LUM Imaging System and to review any SAEs that occur during the study. The DSMB will develop and follow a DSMB Charter. The DSMB will be composed of at least 2 oncology specialists (at least one of whom specializes in surgical oncology) and a statistician. The DSMB will be provided with all reports of adverse events including SAEs regardless of investigator causality assessments.

Following the initial meeting, DSMB meetings will occur on a periodic basis in accordance with the DSMB charter. The chairperson of the DSMB will also be immediately provided with the report of any SAE that is judged as possibly, probably, or definitely attributable to treatment with the investigational product. The charter of the DSMB will specify that this committee is charged with providing periodic reports to Luminicell that contain recommendations that include, but are not limited to, (a) continuation of the study, and (b) termination of the study.

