3.5 Safety measurements analysis

The safety measurements include the following:

- a. Adverse events stratified by severity and relatedness to drug/device
- b. Serious adverse events stratified by severity and relatedness to drug/device
- c. Adverse events by preferred term (sorted by descending occurrences for each preferred term)
- d. Summary of adverse events, overall and split by expectedness to drug/device
- e. Comparison of adverse events in subjects that have at least one therapeutic shave versus subjects that have no therapeutic shaves

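### Protocol 12.1.3 says device effects are not SAEs; taken literally, serious device-related events miss the immediate DSMB chair alert and leave the device-related cells of the SAP's SAE table empty

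*Protocol*

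**What the plan says.** - **Protocol 12.1.2** defines seriousness by outcome alone: "A serious adverse event (SAE) is any adverse event, occurring at any dose and regardless of causality that" meets one of the listed criteria. It makes no exception for device-related events.
- **Protocol 12.1.3** sets no upper limit of severity: "An adverse device effect (ADE) is an adverse event which is at least possibly related to the device". It then adds: "ADEs are not considered serious adverse events".
- **Protocol 12.1.4** defines a UADE as a serious device-associated effect that "was not previously identified in nature, severity, or degree of incidence in the investigation plan or application", and adds a further limb for other unanticipated serious problems. Section 12.4.2 treats UADEs as serious and sends them to the sponsor on the SAE form within 24 hours.
- **Protocol 12.4.3** covers the remainder: "Non-serious adverse events and non-serious adverse device effects will be reported" on the ordinary adverse event forms.
- **Protocol 11.3** states that "there are no known anticipated or expected adverse device effects".
- **Protocol 13.4** gives the DSMB all adverse event reports and adds a faster channel: "The chairperson of the DSMB will also be immediately provided with the report of any SAE" that is attributed to the investigational product. UADEs are not named there.
- **Protocol 15.6** requires SAEs and UADEs to be tabulated separately.
- **SAP 3.5 and 4.5** list "Serious adverse events stratified by severity and relatedness to drug/device" and a matching table for all adverse events. Neither section mentions UADEs.

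**The concern.** An event that meets a seriousness criterion and is rated possible, probable or definite for the device is an SAE under 12.1.2 and not an SAE under 12.1.3. Sites have no rule for choosing between the two definitions, so the same event could be classified differently at different sites.

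Two downstream items depend on the SAE label: the immediate alert to the DSMB chair and the SAP table of SAEs by device relatedness. If 12.1.3 is applied as written, the alert does not fire for such an event. The table then shows no device-related SAEs because the definition excludes them. A reader of the study report could take that zero as evidence about the device.

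**Working it through.** No arithmetic applies. The check follows one type of event through both documents: an adverse event that meets a 12.1.2 criterion and is judged at least possibly device-related, with 12.1.3 taken literally.

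**Step 1: is 12.1.3 the outlier?** Yes. Section 12.4.3 specifies non-serious ADEs, which makes sense only if serious ones exist. Section 12.8 requires follow-up of ADEs of both kinds. The SAP stratifies SAEs by relatedness to the device. All three agree with 12.1.2 and conflict with 12.1.3.

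**Step 2: reporting to the sponsor.** The event loses the SAE label. Because 11.3 lists no expected device effects, a serious one would ordinarily be a UADE, with the same form and the same 24-hour clock. The route is preserved unless the effect counts as previously identified. That could happen in two ways:
- Under 12.1.5.1 an effect can also be expected because it appears in the Investigator's Brochure, the Instructions for Use or the consent form. Those documents are not available here.
- An effect can become identified after a first case. Section 11.2 shows this for the drug: anaphylaxis was reclassified as expected after one patient. If a serious device effect were handled the same way, a second case would be neither a UADE nor, under 12.1.3, an SAE.

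Even this gap may be narrower for the most severe events. The grade list in 12.4.1 includes Grade 4 and Grade 5 events without regard to attribution, so a life-threatening or fatal device effect might still be caught there. The gap is clearest for a serious, already identified effect of Grade 2 or 3.

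**Step 3: DSMB.** The event reaches the board, because 13.4 supplies all adverse event reports whatever the attribution. The immediate alert to the chair does not fire, because its trigger is an SAE and neither UADEs nor serious ADEs are named. Information is delayed, not withheld.

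**Step 4: analysis.**

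| Output | Serious event rated possible or higher for the device |
|---|---|
| SAP 3.5a, all adverse events by severity and relatedness | Appears |
| SAP 3.5b and 4.5, SAEs by severity and relatedness | Absent; the cell is zero by definition |
| Protocol 15.6, separate UADE tabulation | Appears if it is a UADE, but the SAP does not specify this table |

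The 3.5a table does not replace 3.5b. Severity grade is not seriousness, so a Grade 3 event that led to hospitalisation shares a row with Grade 3 events that did not.

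**The case against.** The strongest reply is that one loose sentence would not govern practice. It may have been meant to say that an ADE is not automatically serious, or that ADE is the non-serious class and UADE the serious one. The SAP table and 12.4.3 suggest that the authors did not work from the literal reading. Several safeguards do not depend on the SAE label: the UADE route, the DSMB's receipt of all reports, ongoing review by the Medical Safety Monitor (13.2), immediate notice of life-threatening complications (8.6), and the stopping rules in 8.7 for device-related death and for any event deemed unacceptable. Section 11.3 reports no device effects in 64 patients (15 + 45 + 4).

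Most of this stands, and it limits the consequences. A reader might infer that serious device-related events drop out of expedited reporting altogether, or that the study would report no serious device harm whatever happened. The documents do not support either inference. The UADE route has the same form and clock, and nothing in 12.1.4 excludes an event rated only possible. The table of all adverse events and the UADE tabulation in 15.6 would still show such events.

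The objection does not remove the contradiction. The text states neither charitable reading, and the second leaves a serious but already identified device effect with no class. The safeguards also leave the wording of the chair alert and the content of the SAE table unchanged.

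**Conclusion.** The rule in 12.1.3 is wrong as written. It contradicts 12.1.2, 12.4.3, 12.8 and the SAP's own table. If it is followed, two things are lost: the immediate alert to the DSMB chair for serious device-related events, and a correct count in the device-related cells of the SAE table. The SAP's omission of the UADE tabulation leaves the second loss unrepaired at the analysis stage. Sponsor reporting is affected only for serious effects already identified.

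The documents give no expected number of such events, so the size cannot be expressed as a count. It may be zero in practice. The conclusion assumes that sites or analysts apply 12.1.3 literally. The size of the residual reporting gap depends on what the Investigator's Brochure, the Instructions for Use and the consent form list, which could not be checked. No efficacy metric or sample size depends on the point. The correction is still worth making, because it bears on safety reporting and costs almost nothing.

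**What to change.** 1. **Protocol 12.1.3:** replace the disputed sentence with: *An ADE is not serious by default; an ADE that meets any criterion in 12.1.2 is also an SAE, and is also a UADE if it meets 12.1.4.*
2. **Protocol 13.4:** add *or UADE* after SAE in the sentence on immediate notification of the chair.
3. **SAP 3.5 and 4.5:** add the UADE tabulation required by Protocol 15.6, and state that serious ADEs and UADEs are counted in the table of SAEs by relatedness.

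The same amendment could make clear whether the grade list in 12.4.1 adds to, or narrows, its opening requirement to report all SAEs. The first change closes the residual gap fully only if that opening requirement governs.

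The cost is one replaced sentence, two added words and a short addition to the SAP's safety sections, with possibly a few more expedited reports. Events already recorded as ADEs should be checked once against 12.1.2 so that the SAE table is complete.
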